1.0 Background & Rationale

Symptom burden is a challenge for patients receiving chemotherapy, with nausea/vomiting and anxiety being some of the most common symptoms causing distress. In particular, the burden experience by patients receiving hematopoietic stem cell transplant (HSCT) may far exceed symptom burden experienced by the general oncology population due to extremely high doses of chemotherapy. Hematopoietic stem cell transplant (HSCT), also call bone marrow transplant, is the process of infusing healthy stem cells into the human body to replace damaged cells caused by disease or cancer (“Stem Cell Transplantation”, n.d.). Prior to receiving a HSCT, patients must receive high doses of chemotherapy and/or radiation in order to help decrease the amount of damaged or cancerous cells in the body leaving room for the new cells to reach the bone marrow and grow into cancer free blood cells. Due to high doses of treatment patients receive prior to HSCT, greater than 90% are likely to experience emesis despite the use of anti-emetics (Faiman, 2016).

Chemo-induced nausea, vomiting, and retching (CINVR) is the most severe and interfering symptom experienced by patients (Stricker & Wesmiller, 2015) and affects treatment-related quality of life (Wood, Chapman, & Eilers, 2011). High dose conditioning regimens damage the gastrointestinal mucosa and activate brain receptors, causing impulses to increase heart rate, respiratory rate, and saliva to cause CINVR (Faiman, 2016). CINVR may be more severe in the

delayed phase for patients receiving HSCT, defined as 24 hours after chemotherapy and lasting up to 7 or more days (Flank, 2017). Anxiety and depression are also common symptoms (Seo et al., 2019), due to prolonged hospitalization (4 weeks or more) separating patients from the comfort of their home and social network. Additionally, HSCT may be anxiety provoking as a last-option treatment for some patients that have experienced several treatment failures and cancer relapse(s).

Alternative therapies may be a promising approach to decrease symptom burden post HSCT. A systematic review evaluating effects of alternative therapies in HSCT patients found that mind and body interventions could aid in reducing anxiety, fatigue, and pain (Chakraborty, Savani, Litzow, Mohty, & Hashmi, 2015). Systematic and narrative reviews found that use of inhaled aromatherapy with essential oils decreased nausea/vomiting (Farahani et al., 2019; Keyhanmehr et al., 2018; Toniolo et al., 2021) and anxiety (Boehm et al., 2012; Farahani et al., 2019; Kayhanmehr et al., 2018) in several studies in the general oncology population. Peppermint was a common essential oil used for nausea/vomiting symptoms (Farahani et al., 2019; Keyhanmehr et al., 2018) and lavender was used most frequently for anxiety symptoms (Farahani et al., 2019). Additionally, randomized controlled trials have found statistically significant improvements in anxiety symptoms in participants that received inhaled essential oils compared to control (Blackburn et al., 2017; Ozkaraman et al., 2018). Only one aromatherapy study involving HSCT was identified, which was a randomized controlled trial that did not find aromatherapy benefit in hospitalized children newly diagnosed with acute leukemia (Ndao et al., 2012). Due to the lack of research, there is limited understanding of aromatherapy efficacy in the HSCT population. Research is needed to expand translation of aromatherapy as an evidence-based practice to populations at high risk for treatment-related complications, such as HSCT. Findings from this study will enhance understanding of the efficacy of aromatherapy on symptom burden in the HSCT population.

2.0 Objective(s)

2.1 Primary Objective

The purpose of this study is to evaluate the efficacy of aromatherapy on symptoms of CINVR and anxiety for patients hospitalized for hematopoietic stem cell transplant. The primary aim will be to evaluate the effect of inhaled aromatherapy on CINVR and anxiety symptoms compared to control for 48 hours.

2.2 Secondary Objective

- Evaluate patient satisfaction with aromatherapy at completion of study.
- Evaluate the antiemetic administration between **nausea/vomiting symptom** intervention and control groups during the 48-hour intervention time span.
- Evaluate the number and incidence of unit falls pre and post intervention.

3.0 Outcome Measures

3.1 Primary Outcome Measures

Chemotherapy-Induced Nausea, Vomiting and Retching (CINVR)

CINVR involves three distinct gastrointestinal symptoms (nausea, vomiting, retching) influenced by administration of chemotherapy. Nausea is expressed as an unpleasant

feeling in the throat/epigastrium that can result in expulsion of stomach content, known as vomiting (Rhodes VA, 2001). Retching is the effort to expel stomach contents without success (Rhodes VA, 2001). A review of CINVR instruments identified the Rhodes Index of Nausea, Vomiting and Retching (INVR) was the only instrument that separately assesses all three symptoms (Wood et al., 2011). The INVR will be used to measure CINVR and includes 8 Likert-type items on a 5-point scale, with evidence supporting reliability (Spearman correlation 0.87) and validity (Rhodes & McDaniel, 1999). Completion of the tool will occur at baseline, 24 hour, and 48 hours of intervention.

The primary endpoint for CINVR is the mean INVR score change from (1) baseline to 24 hours and (2) baseline to 48 hours. We anticipate a 30% reduction in the INVR mean score for participants randomized to the intervention group who indicated nausea/vomiting as primary symptom of concern.

Anxiety

Anxiety is excessive or persistent worry about aspects of life ("Understanding the Facts of Anxiety Disorders and Depression is the First Step," n.d.). Anxiety will be measured using a shortened version of Spielberger's State Anxiety Inventory (SAI). The original SAI contains 20 items to measure state anxiety and items are scored using a 4-point Likert-type scale (almost never-almost always) (Spielberger, Gorsuch, Lushene, Vagg, & Jacobs, 1983). The SAI instrument has good internal consistency (.86-.95), test-retest reliability (.65-.75) (Spielberger et al., 1983), and evidence supporting construct and concurrent validity (Spielberger et al., 1983). The shortened SAI retains 6 items (from the original 20) and has evidence supporting good internal reliability consistency (Cronbach's alpha .84) and strong construct validity (Abed, Hall, & Moser, 2011). Completion of the tool will occur at baseline, 24 hours, and 48 hours of intervention.

The primary endpoint for anxiety is the mean shortened SAI score change from (1) baseline to 24 hours and (2) baseline to 48 hours. We anticipate a 30% reduction in the SAI mean score for participants randomized to the intervention group who indicated anxiety as their primary symptom of concern.

3.2 Secondary Outcome Measures

Patient Satisfaction with Aromatherapy

A brief semi-structured questionnaire will also be administered to evaluate patient satisfaction with the intervention at the 48-hour completion time.

Evaluate the antiemetic administration between **nausea/vomiting symptom intervention and control groups**

Data will also be collected from the electronic medical record related to antiemetic medications administered (dose, route, frequency) during the 48-hour intervention.

Evaluate the number and incidence of unit falls pre and post intervention

Fall rates will also be evaluated using the total number of falls reported to the National Database of Nurse Quality Indicators during the baseline and intervention timeframes. Demographic data will be collected including age, gender, and race/ethnicity.

4.0 Eligibility Criteria

Eligibility criteria will be confirmed through review of the electronic medical record and/or patient self-report. Pregnancy tests are standardly completed prior to stem cell transplant and result will be available prior to study enrollment (if applicable).

4.1 Inclusion Criteria

[figure not shown]
- Patients from a bone marrow transplant unit or hematology/oncology unit within an adult academic health center in the Midwest.
- Adult stem cell transplant inpatients that have received autologous or allogeneic transplant and are actively going through therapy.
- Patients must also be alert and oriented, able to interact with the study team, and able to read and write English.

4.2 Exclusion Criteria

- Under 18 years of age
- Currently receiving another form of essential oils (e.g., diffuser, essential oil roller, lotion with essential oils) within 24 hours of enrollment
- Intubation
- Medical sedation
- Receipt of chimeric antigen receptor T (CAR-T) cells
- History of atrial fibrillation
- History of seizures/epilepsy
- Adhesive allergy or sensitivity
- Currently pregnant
- Prisoner
- Inability to smell

5.0 Study Design

This study will be a randomized controlled trial. Prior to randomization, participants will be asked which symptom, nausea/vomiting or anxiety, is most burdensome for them. Participants will be stratified based on their identified symptom of burden (nausea/vomiting or anxiety) and will then be randomized to either the intervention or control group, with a target of 50 participants in the nausea/vomiting symptom group (25 intervention and 25 control) and 50 participants in the anxiety symptom group (25 intervention and 25 control). Intervention and control groups will receive Wyndmere Naturals, Inc. aromatherapy patches and a symptom journal. Participants in the intervention group indicating that nausea/vomiting is the primary symptom of concern will receive peppermint inhaled aromatherapy patches (or mandarin if peppermint intolerance indicated). Participants in the intervention group indicating that anxiety is the primary symptoms of concern will receive lavender inhaled aromatherapy patches. The control group will receive non-scented aromatherapy patches (i.e., blank hydrogel adhesive patches without essential oil infusion), so it will not be feasible to blind participants to group assignment. The control group will have the same interactions with the study team as the intervention group and will complete patch changes and a symptom journal to serve as an attention control.

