6.0 Enrollment/Randomization

Potential participants will receive an information flyer and brief description of the study in clinic prior to stem cell transplant. Flyers will also be available in stem cell transplant classes. The

research team will evaluate the electronic medical record daily for patients meeting inclusion criteria for enrollment into the study on admission. Eligibility will be confirmed on admission and patients meeting inclusion criteria will be approached by the research team for potential study enrollment on post-transplant day 4, 5, 6, 7 or 8. Patients will be approached for potential study enrollment and if interested, will consent and begin study interventions post-transplant day 4, 5, 6, 7, or 8 (depending on day research team approaches). This timeframe will allow the team to observe for delayed CINVR and allow for flexibility in the study schedule to account for patient or study team member unavailability. The study team will provide a summary of the study and will review informed consent and HIPAA authorization documents. Patients that agree to participate in the study will sign a consent and HIPAA authorization. Consented participants will then be randomly assigned using a random number table generated in Microsoft Excel to allocate patients to the intervention or control group.

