After consenting to study participation, patients will complete a brief demographic questionnaire (see Appendix A). Additional patient data (cancer type, chemotherapy regimen, transplant type, unit of hospitalization) will be collected from the electronic medical record by a study team member. Patients will be asked what symptom they find most concerning (nausea/vomiting or anxiety) and will then be randomly assigned to the intervention or control group using a random number table based on symptom of concern. After random assignment, the patient will be educated on how to use a symptom journal (Appendix B) by a study team member and will be asked to complete the baseline symptom measures in the journal. Patients will be instructed to complete the same symptom measures on the following day independently (24 hour follow up). Patients assigned to the intervention group will receive 48 hours (6 patches) worth of essential oil infused (lavender, peppermint, or mandarin) patches. Aromatherapy patches will be applied to the patient's skin containing peppermint, mandarin, or lavender essential oils. Patient indicating that nausea/vomiting is their symptom of concern will receive peppermint as the default oil or mandarin oil if they have a known intolerance to peppermint. Patients indicating that anxiety is their symptom of concern will receive lavender oil. Patients assigned to the control group will receive 48 hours (6 patches) worth of non-scented patches (i.e., blank hydrogel adhesive patches without essential oil infusion). Patients in both groups will be instructed to change the aromatherapy patch (essential oil infused [intervention group] or non-scented [control group]) every 8 hours, as recommended by manufacturer, and document the

patch change in the symptom journal. Patients in both groups will also be instructed to remove the aromatherapy patch and contact the study team with and signs/symptoms of sensitivity to the patch adhesive or essential oil. The study team will post an “aromatherapy in use” sign inside the patient room to notify clinicians that the patient is on study, with instructions to remove the aromatherapy patch before a MRI test.

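### Patients without the symptom they name can be randomised, because nothing before assignment checks that it is present; this can attenuate the primary effects and reduce power

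*Combined protocol and SAP*

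**What the plan says.** Entry is defined by setting and treatment. The clinical inclusion criterion in section 4.1 is "Adult stem cell transplant inpatients that have received autologous or allogeneic transplant and are actively going through therapy"; the others concern the unit, alertness and English. Section 4.2 has no symptom item. On timing, section 6.0 says: "Eligibility will be confirmed on admission and patients meeting inclusion criteria will be approached by the research team", the approach falling on post-transplant days 4 to 8.

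Symptoms first enter through the question in section 5.0: "Prior to randomization, participants will be asked which symptom, nausea/vomiting or anxiety, is most burdensome for them". Section 7.0 repeats it in terms of concern rather than burden. Neither place mentions a minimum severity or what happens if a patient reports neither symptom.

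The scales come later. Section 7.0 reads "After random assignment, the patient will be educated on how to use a symptom journal (Appendix B) by a study team member", and the baseline measures are completed at that step. Section 5.0 acknowledges that participants cannot be blinded.

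The primary endpoints in section 3.1 are changes from baseline. For nausea and vomiting: "The primary endpoint for CINVR is the mean INVR score change from (1) baseline to 24 hours and (2) baseline to 48 hours"; the anxiety endpoint has the same form on the shortened SAI. The expected benefit is a fall in the mean: "We anticipate a 30% reduction in the INVR mean score for participants randomized to the intervention group who indicated nausea/vomiting as primary symptom of concern", and likewise "We anticipate a 30% reduction in the SAI mean score for participants randomized to the intervention group". Section 12.0 analyses each symptom group by a mixed-model ANOVA over the three times, with no restriction to patients symptomatic at baseline.

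**The concern.** The trial asks whether aromatherapy relieves a symptom, but no step confirms that the patient has it. The question identifies the worse of two symptoms, and the worse of two can still be mild or absent. Section 7.0 leaves antiemetics, steroids and benzodiazepines uncontrolled, so some patients may be well controlled when approached. The eligibility check on admission comes too early to see symptoms on days 4 to 8, and the baseline scores come too late to act as a screen.

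A patient who starts near the bottom of the scale has little room to improve in either arm. Enough such patients would shrink the mean difference between arms, and a real benefit in symptomatic patients could be missed. The sample size leaves no slack for this: section 12.0 allows for 10% dropout and nothing else.

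**Working it through.** **Inputs.** From section 12.0: effect size 0.81, 25 per arm in each symptom group, two-sided 5%, two-sample t-test, 80% power, 10% dropout. Assumed, because the documents give no figure: f, the share of patients in each arm of a symptom group who cannot show a treatment difference, taken as 10%, 20% and 30%. Also assumed: 0.81 is the effect in the remaining, symptomatic patients.

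**1. The plan's own figures.** Noncentral-t power at d = 0.81 with 25 per arm is 0.801, and the smallest effect detectable with 80% power is 0.809. Dropout: 50/0.9 = 55.6, so 56 per group, and 100/0.9 = 111.1, so 112 in all. Section 12.0 reproduces.

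**2. Model A, SD unchanged.** The mean effect becomes d = 0.81 × (1 − f).

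| f | d | Power, 25 per arm | Per arm for 80% | Symptomatic effect needed for 80% at 25 per arm, 0.809/(1 − f) |
|---|---|---|---|---|
| 0 | 0.81 | 80% | 25 | 0.81 |
| 10% | 0.73 | 71% | 31 | 0.90 |
| 20% | 0.65 | 61% | 39 | 1.01 |
| 30% | 0.57 | 50% | 50 | 1.16 |

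**3. Model B, exactly zero change in those patients.** The SD now shrinks as well. With unit SD in symptomatic patients and no average change in symptomatic controls, the control variance is 1 − f and the treated variance is (1 − f) + f(1 − f) × 0.81². The standardised effect is 0.81(1 − f) divided by the square root of their average.

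| f | Control variance | Treated variance | Pooled SD | d | Power by formula |
|---|---|---|---|---|---|
| 10% | 0.900 | 0.959 | 0.964 | 0.756 | 0.745 |
| 20% | 0.800 | 0.905 | 0.923 | 0.702 | 0.681 |
| 30% | 0.700 | 0.838 | 0.877 | 0.647 | 0.610 |

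The formula treats the mixture as normal. Simulating it directly gives 0.746, 0.685 and 0.613 with 20,000 runs, and 0.750, 0.688 and 0.618 with 200,000. All three sets agree within one percentage point: about 75%, 69% and 61%. If symptomatic patients in both arms also improve by 0.5 SD, simulated power is 72%, 63% and 54%, between models A and B.

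**4. Link to the planned analysis.** These are t-test calculations, as in section 12.0. The planned mixed model tests a group-by-time contrast, and the same patients dilute that contrast in the same way.

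**The case against.** Much of the other side stands.

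- *The share may be small.* Section 1.0 puts the likelihood of emesis above 90% even with anti-emetics, section 6.0 chose days 4 to 8 to capture delayed symptoms, and a patient with either symptom can name that one. This argues for a small f in the nausea/vomiting group. It is not a prevalence at the day 4–8 approach, and no comparable figure is given for anxiety, which has its own primary test.
- *A reader might infer that patients are forced to choose.* The script of the question is not in the documents, and how staff handle a patient with neither symptom is unstated. The plan is silent; it does not prescribe a forced choice.
- *A reader might infer that the 80% power assumes every patient can respond.* Section 12.0 does not say so. It gives 0.81 as a detectable difference between arms, whoever is enrolled. The power loss follows only if 0.81 is read as the effect in symptomatic patients.
- *A reader might infer that patients at the floor contribute nothing.* They can worsen. If controls worsen and treated patients do not, they add to the difference.
- *A reader might argue that low SAI scores make a 30% fall arithmetically impossible.* Section 3.1 anticipates a fall in the mean score, not a response threshold for each patient, and the documents do not give the item coding that fixes the scale minimum.
- *Broad entry is a legitimate choice.* It is, for an adjuvant to usual care. The plan does not present it as a choice, and it makes no allowance for it in the sample size.

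None of this removes the gap: no listed step requires the symptom before randomisation.

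**Conclusion.** The point holds as a design gap that can cost power. Patients with little or no symptom can enter both primary comparisons; the documents do not show that they will, or in what number. The comparison remains a fair randomised one and type I error is unaffected. The risk is an attenuated effect and a missed benefit.

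The size is conditional on f and on reading 0.81 as the effect in symptomatic patients: power of about 71–75% at f = 10%, 61–69% at 20% and 50–61% at 30%. The lower ends assume an unchanged SD and the upper ends zero change in symptom-free patients; any preventive effect in patients at the floor would reduce the loss. The conclusion also takes the criteria listed in section 4.1 as complete, since a figure there is not visible in the text available. The change is worth making because it is cheap and fits the stated aim, but the gap does not invalidate the trial.

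**What to change.** Amend sections 4.1, 5.0 and 7.0 as follows.

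1. Add an answer to the pre-randomisation question meaning that neither symptom is a problem at present, and do not randomise patients who give it.
2. Move completion of the existing INVR and shortened SAI baseline from after to before random assignment. This reorders steps within visit 1, where section 8.0 already places both consent and the scales. It also stops knowledge of allocation from influencing baseline scores.
3. Randomise only patients whose score on the chosen scale exceeds a minimum that the team sets and justifies. A cut-off just above the bottom of the scale would still leave little room to fall, so the justification matters.
4. Allow patients who screen out to be re-approached within days 4 to 8.

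No new instrument or visit is needed. The cost is screen failures and slower accrual, growing with f. If a share f screens out and none return, randomising 112 means screening 112/(1 − f) willing patients: about 125 at 10%, 140 at 20% and 160 at 30%. Results would then apply to patients who have the symptom.

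If the team prefers broad entry, it should say so, state an assumed f and size the trial for it. Under model A that means 31, 39 or 50 per arm, or 69, 87 or 112 recruited per symptom group after 10% dropout (62/0.9, 78/0.9, 100/0.9), against the 56 planned.

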6.0 Enrollment/Randomization

Potential participants will receive an information flyer and brief description of the study in clinic prior to stem cell transplant. Flyers will also be available in stem cell transplant classes. The

research team will evaluate the electronic medical record daily for patients meeting inclusion criteria for enrollment into the study on admission. Eligibility will be confirmed on admission and patients meeting inclusion criteria will be approached by the research team for potential study enrollment on post-transplant day 4, 5, 6, 7 or 8. Patients will be approached for potential study enrollment and if interested, will consent and begin study interventions post-transplant day 4, 5, 6, 7, or 8 (depending on day research team approaches). This timeframe will allow the team to observe for delayed CINVR and allow for flexibility in the study schedule to account for patient or study team member unavailability. The study team will provide a summary of the study and will review informed consent and HIPAA authorization documents. Patients that agree to participate in the study will sign a consent and HIPAA authorization. Consented participants will then be randomly assigned using a random number table generated in Microsoft Excel to allocate patients to the intervention or control group.

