12.0 Statistical Considerations

SAS and/or R statistical packages will be used to analyze primary outcomes, secondary outcomes, and demographic sample data.

Primary Outcomes

Comparisons between the intervention and control groups for differences in the CINVR and anxiety tools will be analyzed using mixed-model ANOVA, with time (baseline, 24 hours, 48 hours) repeated within subject. Chi-square tests will be used to compare the groups for differences in the proportions of patients prescribed medications for nausea/vomiting or anxiety. Separate analyses will be performed for the two symptom groups. A two-sided 5% significance level will be used for all tests.

Sample size justification: With sample sizes of 50 patients within each symptom group, 25 intervention/25 control within each symptom group, the study will have 80% power to detect an effect size of 0.81 between intervention and control within each symptom group, based on a two-sample t-test calculation and a two-sided 5% significance level. The recruitment target will be 112 participants (56 per symptom group) to account for a 10% drop out rate.

Secondary Outcomes

Descriptive statistics will be used to analyze frequencies and percentages of the patient satisfaction questionnaire responses, documented antiemetic administration, and number of unit falls. The number of (1) total antiemetic medication doses and (2) doses for each individual medication (i.e., Ativan, promethazine) will be compared between the control and intervention groups for the nausea/vomiting symptom group. The percentage change for number of falls will be calculated by comparing number of falls 12 months prior to intervention implementation to 12 months during implementation.

Descriptive statistics will be used to summarize the demographics of the study sample (frequencies and percentages for categorical variables, means and standard deviations for continuous variables).

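### Allocation is from an Excel random number table with no stated restriction or concealment, and the self-reported baseline is completed after assignment although participants cannot be blinded

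*Combined protocol and SAP*

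**What the plan says.** **Method.** Section 6.0 has consented participants "randomly assigned using a random number table generated in Microsoft Excel to allocate patients" to intervention or control. Section 7.0 adds that, after naming their main symptom, they are "randomly assigned to the intervention or control group using a random number table based on symptom of concern". That is the whole description. Nothing is said about blocking or other restriction, who prepares or holds the table, or how the next entry is hidden until a patient is committed.

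**Numbers.** Section 5.0 sets a "target of 50 participants in the nausea/vomiting symptom group (25 intervention and 25 control"), and the same for anxiety. Section 12.0 states that, with those numbers, "the study will have 80% power to detect an effect size of 0.81 between intervention and control within each symptom group". It recruits 56 per symptom group to allow for 10% dropout.

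**Blinding and timing.** Control patches carry no scent, "so it will not be feasible to blind participants to group assignment" (Section 5.0). Consent and start can fall on any of post-transplant days 4 to 8, "depending on day research team approaches" (Section 6.0).

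**Order at visit 1.** Section 7.0 runs: consent, symptom choice, random assignment, journal teaching, baseline symptom measures. Section 3.1 defines both primary endpoints as change from that baseline to 24 and to 48 hours. The sample journal in Appendix B shows a field for the oil given on the same sample page as the space for the measurement tool.

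**The concern.** Participants know whether their patch is scented and score their own symptoms. Concealing the allocation until a patient is committed is therefore the main protection left against selection bias, and the plan does not describe it. The research team screens records daily and has a five-day window in which to approach. Someone who could read the table would have room to time an approach to suit the next assignment.

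The order in Section 7.0 is a separate matter and does not depend on who sees the table. A patient who knows the arm before scoring the baseline may score it differently, in a direction that cannot be predicted. That score is the reference for both primary changes and the first time point in the mixed model of Section 12.0.

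The 25/25 split behind the power statement is also a target with no stated mechanism for reaching it.

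**Working it through.** **1. The plan's own figures.** Inputs from Section 12.0: 25 per arm, standardised effect 0.81, two-sided 5%, two-sample t-test, 10% dropout.
- Noncentrality = d × √(n1·n2/(n1+n2)) = 0.81 × √(625/50) = 0.81 × 3.536 = 2.864, with 48 degrees of freedom.
- Exact noncentral-t power = 80.1%. The stated 80% is reproduced.
- 50/0.9 = 55.6, so 56 per symptom group, and 2 × 56 = 112. Both are as stated.

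**2. Balance, if the table is unrestricted (an assumption).** The number in one arm of 50 is Binomial(50, 0.5).
- P(exactly 25/25) = C(50,25)/2^50 = 11.2% in one symptom group; in both, 0.1123² = 1.3%.
- P(20/30 or worse) = 20.3% in one group; in at least one of the two, 1 − (1 − 0.2026)² = 36.4%.
- With 56 allocated: P(28/28) = 10.6%, and P(one arm is allocated fewer than 25) = 35.0% before any dropout.

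**3. What imbalance costs.** Same formula, total of 50:

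| Split | Noncentrality | Power |
|---|---|---|
| 25/25 | 0.81 × √(625/50) = 2.864 | 80.1% |
| 20/30 | 0.81 × √(600/50) = 2.806 | 78.5% |
| 18/32 | 0.81 × √(576/50) = 2.749 | 76.9% |

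Averaged over the binomial distribution, power is 79.3%, a loss of 80.1 − 79.3 = 0.8 points.

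**4. Predictability.** Share of assignments guessed correctly by someone tracking past assignments (simulated where the list is restricted):
- hidden unrestricted list: 50%
- hidden 25/25 list permuted as a whole: about 58%
- fixed blocks of 6: about 68%
- fixed blocks of 4: about 71%
- fixed blocks of 2: about 75%

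A list that can be read gives every assignment away, whatever its structure. Access to the table is therefore what matters most, and small fixed blocks would buy balance at some cost in predictability.

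**5. How each bias reaches the endpoint.** The difference in mean change is (F_I − B_I) − (F_C − B_C), where B is the baseline mean, F the follow-up mean, and I and C the two arms.
- *Selection.* If foreknowledge makes one arm worse by δ at both baseline and follow-up, δ cancels. Only a difference in expected course remains.
- *Baseline scored with the arm known.* If B_I alone is shifted by δ, the difference in change is shifted by −δ at 24 hours and again at 48 hours. Nothing cancels.

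**6. Illustration only.** Suppose a pure bias of 0.2 or 0.3 SD in a two-sample t-test at 25/25, with no treatment effect. Noncentrality is 0.2 × 3.536 = 0.707 or 0.3 × 3.536 = 1.061, and the rejection rate is 10.7% or 18.0% instead of 5%. The documents give no source for shifts of this size, and this is not the planned repeated-measures analysis.

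**The case against.** The strongest reply is that the plan is brief on this point rather than wrong. An Excel table can be a permuted 25/25 list for each symptom group, and the text nowhere calls it unrestricted. The 25/25 split is worded as a target. Assignment is described in the passive, so no section says who reads the table. Only participants are stated to be unblinded. The day 4 to 8 window has stated reasons: to observe delayed symptoms and to allow for patient or staff unavailability. Consent and symptom choice already precede assignment, and the patient names the symptom.

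Most of this stands. It rules out three inferences that a reader might draw:
- *The method fails to give 25/25.* Not shown. It does not guarantee it.
- *Staff foresee or steer assignments.* Not shown. The text leaves it possible, and only if they can see the table.
- *The false-positive rate is 11% or 18%.* Not supported. The shifts are assumed, and a stable prognostic difference cancels in a change score.

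The reply does not reach the order of baseline and assignment, which Section 7.0 states outright. It could be said that a patient might be assigned but not yet told when scoring the baseline. No section provides for that.

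**Conclusion.** The point holds in a limited form and should be corrected. The stated method includes no restriction and no concealment, in a trial with unblinded participants, self-reported endpoints and an approach day set by the team. It does not secure the 25/25 target, and it permits foreknowledge if enrolling staff can see the table. The stated order also allows knowledge of the arm to affect the baseline score, and any such effect passes in full into both primary change scores.

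The cost in power is small: under 2 points at 20/30 and 0.8 points on average, assuming simple randomisation of 50 per symptom group. The reason to act is bias. Its size cannot be estimated from the documents, and the planned analysis could not reliably remove it afterwards.

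**What to change.** Amend Sections 5.0 to 7.0 as follows:
- Replace the Excel table with two 1:1 permuted-block lists, one per symptom group, with varying block sizes (for example 4 and 6) not disclosed to enrolling staff.
- Have the lists prepared by someone not involved in enrolment, such as the statistician, and loaded into the REDCap system that the study already uses.
- Reorder visit 1 in Section 7.0 so that consent, eligibility, symptom choice and the baseline INVR and SAI are all saved before the arm is revealed.

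The cost is about one paragraph of text and a short REDCap set-up. Section 13.0 has journal data transferred from paper, so baseline scores would need to be entered during visit 1. No visit or measure is added. Some guessing at the end of a block remains possible because past assignments are visible; varying, undisclosed block sizes limit it.
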